8.3.4 Stage 4: 24-48 hours post PCI

Full written consent to take part to the OxAMI-PICSO study is obtained as soon as practicable. The following study assessments may be carried out:

1. Repeat coronary angiogram for assessment of coronary physiology parameters assessment – for participants who receive the PICSO device only
2. Cardiac magnetic resonance - for participants who receive the PICSO device only
3. Venous blood sampling for biomarker measurement
4. Data Collection, Patient Reported Outcomes and Cardiovascular Outcomes

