5. OBJECTIVES AND OUTCOME MEASURES/ENDPOINTS

Objectives	Outcome Measures/Endpoints
------------	----------------------------

Primary Objective
 
To assess the impact of PICSO on coronary physiology parameters, on infarct size, on myocardial salvage and on microvascular obstruction at CMR in a selected population of STEMI patients at higher risk of no reflow and with the theoretical prerequisites that make more likely to respond to PICSO treatment. The control group will be represented by a highly matched group of patients from the ongoing Ox-AMI (Oxford Acute Myocardial Infarction) project (Ethics Ref 11/SC/0397), who have undergone all other aspects of the study protocol, including assessment of coronary physiology at 24 hours post primary PCI, 24-48 hours and 6 months CMR, but who have not received PICSO treatment.
	
Area at risk, Infarct size, Myocardial salvage and microvascular obstruction measured by cardiac magnetic resonance at 24-48 hours

Secondary Objectives
 
The OxAMI-PICSO study aims to evaluate the utility of individual biomarkers (blood components derived substances from cells, DNA, plasma etc) in the assessment of coronary artery disease and myocardial infarction. The OxAMI-PICSO may show also how these individual biomarkers may be modified by PICSO treatment.
	
Coronary flow reserve (CFR), Fractional Flow reserve (FFR), index of microcirculatory resistance (IMR) measured at 24 hours after PCI.
 
Infarct size and microvascular obstruction extent measured by cardiac magnetic resonance at 6 months
 
Individual Biomarkers related to coronary artery disease/myocardial infarction at three time points (PCI, 24/48 hours after PCI and 6 months). These include: blood biomarkers of myocardial injury, metabolism and inflammation.

Tertiary Objectives
 
To evaluate the rate of PICSO failure deployment, coronary sinus complications, and additional time and radiation exposure associated to for PICSO deployment
	
Rate of PICSO failure deployment
 
Rate of coronary sinus complications: perforation, dissection, thrombosis
 
Time for PICSO deployment / additional screening time and radiation dose

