6. TRIAL DESIGN

The OxAMI-PICSO study is a prospective single centre observational cohort study of the use of PICSO in patients presenting for primary PCI for acute myocardial infarction. The OxAMI- PICSO study is based upon the established framework of the OxAMI study (Ethics Ref 11/SC/0397).

Patients, age 30-90, presenting with ST elevation myocardial infarction will be considered for inclusion in the study. Measurement of IMR before stenting is an essential prerequisite for the study: only patients with pre-stenting IMR > 40 will be considered eligible for the PICSO treatment. Patients with IMR≤ 40 will remain in the study but will not undergo PICSO treatment. The procedure for consent in patients undergoing emergency PCI will be as already established in the ongoing OxAMI study, and is discussed below in Section 8.1.2.

The PCI procedure will be undertaken in a standard fashion, and include the use of pressure wire measurements before and after stent deployment. Aspiration or distal protection devices may be used if clinically indicated and where vessel anatomy is suitable. The devices used and the procedural techniques will be driven by clinical decision making at the patient and institutional level, and carried out in accordance with the Oxford University Hospitals NHS Trust (OUHT) departmental guidelines for PCI.

PICSO treatment will be added on top of the conventional treatment.

The protocol will constitute of 5 main stages described in details in the next sections (Section 8.3).

Only patients with pre-stenting IMR > 40 and who assent to receive PICSO treatment will undergo 24 hours coronary angiogram with coronary physiology measurement, 24-48 hours CMR scan and 6 months CMR scan. Patients who assent to participate in the study but in whom the pre-stenting IMR ≤ 40, or those in whom the pre-stenting IMR > 40 but the participant declines PICSO treatment will remain in the study for blood sampling and clinical data collection at the same follow up time points (24 hours, 48 hours and 6 months). A summary of the study design, indicating the time points and procedures, is shown in Section 8.3.

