8.3.5 Stage 5: 6 months post PCI

Participants will be invited to attend the hospital as an outpatient at approximately 6 months post-PPCI for the following research assessments

1. Cardiovascular MRI - for participants who receive the PICSO device only
2. Blood sampling for biomarker measurement
3. Data Collection, Patient Reported Outcomes and Cardiovascular Outcomes

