12.2 Analysis of Endpoints

In keeping with our usual practice we will obtain expert statistical advice from the Centre for Statistics in Medicine (or equivalent) for each specific task. Summary statistics, including means, medians, and

variances, will be calculated at each time point and for each type of data (e.g. parameters derived from coronary physiology and CMR). The distribution of the levels will be described. It may be necessary to log transform the data before further statistical analysis. For each parameter an analysis of variance will be carried out at each time point.

Control group in OxAMI-PICSO study is represented by a highly matched group of patients underwent to primary PCI, with a prestenosing IMR > 40 and with available 24 hours recath and 24-48 hours/6 months CMR data. Matching will be performed by application of a propensity score matching analysis including the following predictors in the model: age, sex, pain to wire time, thrombotic burden (assessed as angiographic thrombus score), thrombus aspiration performance, stent volume, glycoprotein IIbIIIa inhibitors adoption.

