20. APPENDIX A: SCHEDULE OF PROCEDURES IN PICSO GROUP

Procedures	Pre-PCI	PICSO group					6 hours	24 hours	48 hours	6 months				
		During PCI												
		Start of procedure	PICSO start	End of PCI	PICSO stop									
Verbal assent	X													
Blood samples		X	X	X	X	X	X	X	X	X				
PICSO			X	X	X									
Coronary physiology measurements (IMR, CFR, FFR)		X		X		X								
Informed written consent						X								
Coronary angiogram with coronary physiology measurements (IMR, CFR, FFR)								X						
CMR									X	X				
ECG	X			X		X								
Echocardiography								X						
Medical history Demographic data collection									X					

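### A patient who assents to PICSO but whose catheter placement fails gets the primary-endpoint CMR under section 6 and not under 8.3.4/8.3.5, and 12.2 names no treated set

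*Combined protocol and SAP*

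**What the plan says.** Section 6 (Trial Design) sets follow-up by IMR and assent: "Only patients with pre-stenting IMR > 40 and who assent to receive PICSO treatment will undergo 24 hours coronary angiogram", and the same sentence adds the 24-48 hour and 6-month CMR scans. It moves two groups to a lighter schedule. One is patients with IMR of 40 or less. The other is those above 40 where the participant "declines PICSO treatment will remain in the study for blood sampling and clinical data collection".

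Sections 8.3.4 and 8.3.5 set follow-up by receipt of the device. At 24-48 hours the rule is "Cardiac magnetic resonance - for participants who receive the PICSO device only", and the repeat angiogram carries the same limit. At 6 months it is "Cardiovascular MRI - for participants who receive the PICSO device only".

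Section 5 makes CMR at 24-48 hours the primary outcome and lists the "rate of PICSO failure deployment" among the tertiary objectives. I read this as failed placement of the catheter.

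Appendix A is headed "SCHEDULE OF PROCEDURES IN PICSO GROUP" and has a CMR row. Appendix B covers a non-PICSO group and has none. Neither says where a failed placement belongs.

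Section 12.2 defines the controls as primary PCI patients "with a prestenosing IMR > 40 and with available 24 hours recath and 24-48 hours/6 months CMR data", matched by propensity score on "age, sex, pain to wire time, thrombotic burden (assessed as angiographic thrombus score), thrombus aspiration performance, stent volume, glycoprotein IIbIIIa inhibitors adoption". It does not define the treated patients who are compared with them. Section 8.4 stops recruitment once 25 participants have had PICSO and completed 6 months.

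**The concern.** The two rules give different answers for one foreseeable patient: IMR above 40, assent given, placement attempted and failed. If staff follow 8.3.4, this patient has no infarct-size measurement, and a scan missed at 24-48 hours cannot be made up later.

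The treated group then consists only of patients in whom delivery succeeded. The historical controls had no attempt, so those in whom it would have failed are still among them. None of the seven matching predictors measures coronary sinus access or another reason for failed delivery. Matching therefore removes this selection only as far as those predictors happen to capture it. Because 12.2 does not say who counts as treated, that choice, including how to handle shortened delivery, could also be made after results are known.

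**Working it through.** **Step 1. The rules side by side.**

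| Patient | Section 6 | 8.3.4 / 8.3.5 | Appendices |
|---|---|---|---|
| IMR 40 or less | no CMR | no CMR | B |
| IMR above 40, declines | no CMR | no CMR | B |
| IMR above 40, assents, device delivered | CMR | CMR | A |
| IMR above 40, assents, placement fails | CMR (assented; not in either group moved to blood sampling) | no CMR | not placed |

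Only the last row disagrees. The flowchart announced in 8.3 is not in the text available. It might route this patient, but the written rules would still differ.

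**Step 2. Is a failure rate given?** No. Sections 4.2 and 12.1 say the earlier STEMI study of the device fully treated 12 patients and call this 63% of a planned cohort of 30. But 12/30 = 40%, and 63% fits 12/19. Either way the figure concerns full treatment, not failed placement. The 12.1 allowance (75 recruited for 25 complete) names refusal of recatheterisation or MRI, not failed deployment.

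**Step 3. Is there a plan figure to reproduce?** Not for this point. The initial 12 per group in 12.1 cannot be checked, because no SD or control mean is given. The conflict does not depend on it. Only the planned 29% reduction is used below.

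**Step 4. Patients affected.** Let f be the share of attempts that fail, assumed 5-20%. Attempts needed for 25 deliveries = 25/(1 − f), rounded up.

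- f = 5%: 25/0.95 = 26.3, so 27 attempts, 2 failed, 4 scans at two each
- f = 10%: 25/0.90 = 27.8, so 28 attempts, 3 failed, 6 scans
- f = 20%: 25/0.80 = 31.25, so 32 attempts, 7 failed, 14 scans

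**Step 5. Selection if failures are left out (illustration).** Let d be the excess in untreated infarct size of failed over successful patients, in points of the control mean. Suppose the controls resemble all attempted patients. Then mean(successes) = mean(all attempted) − f × d, so with no PICSO effect the treated group shows an apparent reduction of f × d.

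- f = 5%, d = 10: 0.05 × 10 = 0.5 points
- f = 10%, d = 20: 0.10 × 20 = 2 points
- f = 20%, d = 30: 0.20 × 30 = 6 points
- f = 10%, d = −20: 0.10 × (−20) = −2 points, which hides benefit

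No document gives d or its sign.

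**Step 6. Dilution if failures are included.** With no effect where nothing was delivered, the planned 29 becomes 29 × (1 − f): 27.55, 26.1 and 23.2 at f = 5, 10 and 20%.

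**Step 7. Both together.** At f = 10%, d = 20 and a true effect of 29 in delivered patients, the delivered set shows 29 + 2 = 31 and the all-attempted set 26.1. They answer different questions, and neither can be worked out from the other unless the failures are scanned.

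**The case against.** The strongest reply is that there is no real conflict. In section 6 the word 'only' can be read as a necessary condition, which 8.3.4 and 8.3.5 then narrow. The authors may also use receiving the device loosely: 8.3.1 invites patients to receive it, and 8.1.1.1 contrasts them with those who choose not to. Section 8.3.4 is itself permissive. This is fair on intent, but it does not settle the case. On the narrowing reading a failed placement goes unscanned; on the loose reading it is scanned; nothing in the available text chooses between them.

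Second, 8.4 and 12.1 count patients who were treated and completed follow-up, which points to a treated-completer comparison. That is defensible in a single-centre phase II study with historical controls. A reader might infer that all attempted patients must form the primary set. The documents do not support that: it is a choice of question, and in two of the three scenarios above dilution (1.45 and 2.9 points) exceeds the selection effect (0.5 and 2). What stands is that 8.4 and 12.1 set recruitment targets and do not define an analysis set.

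Third, the controls are filtered too, since 12.2 requires recatheterisation and CMR data. That is a filter on completeness, not on delivery.

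Fourth, section 11.9 undertakes to minimise radiation and contrast at the non-routine repeat catheterisation, so limiting that test to device recipients may be deliberate. This stands in full. The angiogram (5 + 1.6 = 6.6 mSv with IMR) is not needed for the primary endpoint.

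**Conclusion.** The point holds as a conflict over who receives the primary-endpoint scan, together with an undefined treated set in 12.2. Followed as written, 8.3.4 leaves failed placements without the primary endpoint and makes the treated group conditional on delivery, which the controls are not. At an assumed 5-20% failure rate this concerns 2 to 7 patients.

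A reader might infer that the comparison is biased in favour of PICSO by a known amount. The documents do not support that. They give no failure rate and no link between failed coronary sinus placement and infarct size, so the 0.5 to 6 points are illustrations and the sign can reverse. A reader might also bring in the 90-minute limit in 10.2 for repositioned patients. It has no bearing on who is scanned or analysed and is not part of this point.

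The change is worth making because it is cheap and the 24-48 hour scan cannot be recovered. Confidence is medium: the flowchart is not available and the authors may have meant one group throughout.

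**What to change.** 1. **CMR eligibility.** In 8.3.4 item 2, 8.3.5 item 1 and the CMR row of Appendix A, follow section 6. Offer CMR to every patient with IMR above 40 who assents and in whom deployment is attempted, including failed or shortened delivery. Define an attempt, for example as insertion of the PICSO delivery sheath. Keep the 24-hour research angiogram for device recipients, and amend section 6 to say so.
2. **Analysis (12.2).** Name the treated set before results are seen, and say whether delivery below the 60-minute minimum in 8.3.2 belongs to it. Report infarct size against matched controls both for patients who received PICSO and for all attempted patients with a 24-48 hour CMR. Give the numbers attempted, failed and not scanned. Which set is primary is the sponsor's choice.
3. **Stopping (8.4).** State that only patients in whom PICSO was delivered count toward the 25, using the same definition as 12.2.

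Cost: wording, two CMRs per failed deployment (about 4-14 scans at the assumed 5-20%), and, if matching is one to one, 2-7 more controls from a pool whose size is not stated. The all-attempted estimate is diluted as shown. The 24-hour physiology comparison remains limited to delivered patients. The fix itself adds no recruitment, since the target of 25 delivered treatments is unchanged.

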8.3.5 Stage 5: 6 months post PCI

Participants will be invited to attend the hospital as an outpatient at approximately 6 months post-PPCI for the following research assessments

1. Cardiovascular MRI - for participants who receive the PICSO device only
2. Blood sampling for biomarker measurement
3. Data Collection, Patient Reported Outcomes and Cardiovascular Outcomes

8.4 Definition of End of Trial

Recruitment to the study will cease as soon as 25 participants have undergone PICSO treatment and have completed follow-up at 6 months. The study will end on the date of the last CMR at 6 months follow up of the last participant recruited.

9. STUDY ASSESSMENT

9.1 Data Collection, Patient Reported Outcomes and Cardiovascular Outcomes

Data on the clinical procedures and any devices and/or imaging technologies used will be collected. Medical history will be taken from the patient once informed consent has been given and relevant sections of the medical notes may be accessed by the study team. Clinical outcomes and MACE will be ascertained during the follow-up appointment with the patient, by accessing relevant sections of the medical notes, ONS database and existing databases of cardiac outcomes and treatment (such as the CCAD and MINAP databases), or by contacting the GP if appropriate.

9.2 PICSO device

See Section 10

9.3 Analysis of CMR

Cardiac related parameters will be derived for further analysis. Analyses will be performed according to published methods and will be focused on the assessment of different cardiac components including anatomy, function, tissue, flow and metabolism (i.e. ventricular volumes, wall motion, infarct size, area at risk, myocardial salvage and microvascular obstruction) [23]. These parameters are partly used both clinically and in research settings (e.g. heart volumes, myocardial mass).

9.4 Analysis of cardiac physiological measurements

Cardiac and/or coronary flow and pressures will be measured, before and after stenting and during the repeat coronary angiogram at 24 hours post-PPCI, using commercially available measurement guidewires

according to standard techniques that are in routine use in current PCI practice. The guidewire contains a pressure-temperature sensor to allow for calculation of the physiological parameters. The guide wire is calibrated at the beginning of the PCI and then advanced into the distal third of the culprit artery. Calculations will be based on measurements of proximal and distal coronary pressure(s) and mean transit time (in seconds) during maximal hyperemia, as previously described. Briefly a pressure wire (Radi; St Jude Medical, St Paul, MN, USA) is placed in the LAD distal to the lesion. Baseline mean aortic pressure (Pa), mean distal pressure (Pd) and Pd/Pa ratio will be recorded. Thermodilution-based measurement of CFR and IMR will be performed by injecting in the IRA 5 ml of room temperature saline solution and recording mean transit time (meanTt) at baseline and after induction of maximal hyperaemia by intravenous infusion at a rate of at a rate of 140 mg/kg/min. Once hyperaemia is achieved the following parameters will be obtained: FFR (Pd/Pa during hyperemia), CFR (meanTtbaseline/meanTthyperaemia) and IMR (Pdhyperaemia* meanTthyperaemia).

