7.3. Exclusion Criteria

The participant may not enter the study if ANY of the following are known to apply:

- Patients in whom safety or clinical concerns preclude participation.
- Known anaemia (Hb <9).
- Pregnant or breast feeding females.
- Revascularization by mean of balloon angioplasty without stenting
- History of stroke, TIA or reversible ischemic neurological disease within last 6 months
- Known severe renal failure (eGFR < 30 ml/min/1.73m²) or history of dialysis or renal transplant
- Previous coronary bypass artery grafting
- Known severe valvular abnormalities
- Previous STEMI presentation
- Presentation with cardiogenic shock
- Severe bradycardia (Heart rate < 50 beats per minutes)
- STEMI due to stent thrombosis
- Unconscious on presentation

- Non-cardiac comorbidities and life expectancy < 1 year
- Use of warfarin
- Presence of pacemaker or other electrodes in the coronary sinus
- Contraindications to adenosine
- Additional exclusion criteria for participants undergoing CMR
 - claustrophobia which limits / prevents participants from remaining in CMR scanner.
 - patients who cannot lie flat on the scan table.
 - patients with metallic implants, pacemakers, implantable defibrillators etc, unless known to be CMR compatible.
 - patients with known allergy to medium of contrast (gadolinium)

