8.3.1 Stage 1: Pre-Stenting

- Diagnostic angiography will be performed in the standard manner using appropriate catheters.
- Bivalirudin will be administered (0.75mg/kg bolus followed by an infusion of 1.75 mg/kg/min for up 4 hours after the procedure as clinically warranted), as routinely used for PCI. The lesion will be

crossed with a coronary guide wire in the usual manner for PCI. Normal blood flow will be rapidly achieved by thrombus aspiration and/or predilation

3. Pre-stenting coronary physiology parameters, namely FFR, CFR and IMR, will be measured, using a pressure wire, as used for routine clinical measurements in patients undergoing PCI.
4. If pre-stenting IMR is > 40 , patients will be invited to receive the PICSO device. If pre-stenting IMR is ≤ 40 PICSO device will not be proposed, but the patient will be invited to remain in the study for serial blood sampling (procedural-6 hours-24 hours and 48 hours) and routine clinical data collection.

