16.11 Potential Benefits

The information derived from coronary pressure/flow measurements is often very useful to the interventional cardiologist in optimising PCI strategy, and the use of vasodilators (e.g. adenosine) as part of the coronary pressure/flow measurements often results in useful clinical improvements in coronary flow.

Finally PICSO treatment, according to pre-clinical literature evidences, is expected to provide a benefit in terms of infarct size reduction. According to animal models this advantage should amount around a 29% in reduction of the infarcted area. The application of PICSO treatment in a highly selected, high risk population of STEMI patients should amplify the potential benefits of this therapy.

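### Two infusion rates in the trial procedures are implausible as printed: bivalirudin in Section 8.3.1 (probable time-unit error) and, subject to a check of the source PDF, the hyperaemia infusion in Section 9.4

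*Combined protocol and SAP*

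**What the plan says.** Two lines in the operative procedures give a weight-based infusion rate.

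- **Section 8.3.1 (Stage 1: Pre-Stenting):** "Bivalirudin will be administered (0.75mg/kg bolus followed by an infusion of 1.75 mg/kg/min for up 4 hours after the procedure as clinically warranted". The section adds that this is routine for PCI.
- **Section 9.4 (Analysis of cardiac physiological measurements):** mean transit time is recorded at baseline and "after induction of maximal hyperaemia by intravenous infusion at a rate of at a rate of 140 mg/kg/min". The sentence names no drug. The section also says that the measurements are made "according to standard techniques that are in routine use in current PCI practice".

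The hyperaemic agent can be inferred from two other places, neither of which gives a dose. Section 7.3 excludes patients with "Contraindications to adenosine", and Section 16.11 mentions "the use of vasodilators (e.g. adenosine) as part of the coronary pressure/flow measurements". Nothing elsewhere in the document repeats, corrects or contradicts either rate.

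**The concern.** A bolus followed by an infusion makes sense only if the bolus supplies something that the infusion would take time to build up. In Section 8.3.1 the infusion as printed overtakes the bolus within half a minute, so the line does not make sense on its own terms. In Section 9.4 the printed rate amounts to grams of an intravenous vasodilator per minute, which is implausible on its face.

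These are instructions for patients with acute STEMI, not background text. Bivalirudin is part of Stage 1, before patients are divided by IMR. Hyperaemia is needed for the pre-stenting IMR, and Section 9.4 repeats the measurements after stenting and at the 24-hour angiogram. Section 14 commits the trial to the approved protocol, with monitors checking compliance. If the source reads as printed here, a safe dose departs from the approved text, and any order set or worksheet copied from that text would carry an unsafe rate.

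**Working it through.** Both rates are inputs that the plan does not derive, so there is no calculation of the plan's to reproduce. The check is unit arithmetic.

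**Inputs**
- Bolus 0.75 mg/kg, infusion 1.75 mg/kg/min, up to 4 h (240 min) after the procedure: Section 8.3.1.
- Hyperaemia infusion 140 mg/kg/min: Section 9.4.
- Body weights of 50, 70 and 90 kg: an assumption, because the documents give none.

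**Section 8.3.1 as printed**
- Boluses per minute: 1.75 / 0.75 = 2.33.
- Time to deliver one bolus-equivalent: 0.75 / 1.75 × 60 = 25.7 s.
- Dose over 4 h: 1.75 × 240 = 420 mg/kg.
- In bolus-equivalents: 420 / 0.75 = 560.
- In grams: 420 mg/kg × 50, 70 and 90 kg = 21.0, 29.4 and 37.8 g.

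The first two results need neither a body weight nor a duration. The 4-hour totals are for the longest post-procedure infusion that the line allows.

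**Section 8.3.1 under other units (neither is in the documents)**
- Per hour: 1.75 × 4 = 7 mg/kg over 4 h, or 7 / 0.75 = 9.3 boluses. The printed rate is then 420 / 7 = 60 times too high.
- Micrograms per minute: 1.75 × 240 = 420 micrograms/kg = 0.42 mg/kg over 4 h, or 0.42 / 0.75 = 0.56 of one bolus.

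**Section 9.4: rate × weight**

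| Assumed weight | As printed (mg) | If micrograms (assumption) |
|---|---|---|
| 50 kg | 140 × 50 / 1000 = 7.0 g/min | 7.0 mg/min |
| 70 kg | 140 × 70 / 1000 = 9.8 g/min | 9.8 mg/min |
| 90 kg | 140 × 90 / 1000 = 12.6 g/min | 12.6 mg/min |

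The factor of 1,000 between the last two columns is the ratio of the assumed unit to the printed one. It is not an error measured against a dose stated in the documents, because none is stated.

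**Could the unit in 9.4 be a reading fault?** In text extracted from a PDF, a micro sign can come out as m. This text does contain character faults: the device name is printed with a zero for its last letter in the Synopsis and Section 17.1, and Section 8.1.1.1 shows raw markup for the less-than-or-equal sign. Other special characters survive (the degree sign in 9.6, the superscript in 7.3, the less-than-or-equal sign in 6). No micro sign appears anywhere, so whether one would survive cannot be tested. The question stays open until the source is read.

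**The case against.** The strongest case against this point concerns Section 9.4. The suspected fault there is a single character, and a micro sign misread as m would give exactly this text without any error in the plan. That stands, and it is why the 9.4 claim is conditional. The missing drug name is editorial, since Sections 7.3 and 16.11 point to adenosine.

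The same artefact cannot be wholly excluded for Section 8.3.1, because 1.75 micrograms/kg/min would not be absurd by arithmetic alone. It is a less ready explanation there: the bolus in the same line is in mg/kg, and changing the time unit alone removes the implausibility. So 8.3.1 is the firmer of the two, but still probable and not proven.

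The practical objection also stands. Both sections refer to routine practice, and Section 11.9 describes pressure-wire studies as routine during PCI. Trained operators would probably not take a dose from these lines. No order set or worksheet is mentioned.

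Three stronger readings are tempting, and the documents do not support them:

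- **That the bivalirudin line proves the error in 9.4.** It concerns a different drug, a different section and, probably, a different kind of unit (time, not mass). It cannot show what the source of 9.4 says, or how the doses were checked in drafting.
- **That patients were given these rates.** Nothing in the documents shows that anyone was.
- **That treatment selection is compromised.** Section 6 says "only patients with pre-stenting IMR > 40 will be considered eligible for the PICSO treatment", and IMR is computed from hyperaemic pressure and transit time. A misprinted rate would matter to that threshold only if it were used, and 9.4 defers to standard technique.

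**Conclusion.** The point holds as a minor patient-safety correction. The bivalirudin rate in Section 8.3.1 is implausible as printed: one bolus-equivalent every 26 seconds, and 560 over 4 hours. The time unit is probably wrong, by a factor of 60 if hours were intended, which is an assumption. The hyperaemia rate in Section 9.4 is a probable mass-unit error at 7.0 to 12.6 g/min for assumed weights of 50 to 90 kg, on condition that the source PDF shows mg. The documents do not give the correct rate for either drug, so this review does not supply one. Eligibility, the IMR threshold, endpoints, sample size and analysis are not affected.

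**What to change.** 1. In Section 8.3.1, read the line in the source PDF and correct the infusion unit to the rate verified by pharmacy.
2. In Section 9.4, read the line in the source PDF. If it shows mg, correct it to the rate verified by the sponsor and pharmacy. In either case name adenosine in that sentence, once the sponsor confirms it is the agent, and delete the repeated phrase before the rate.
3. Check any order set, worksheet or other dosing document derived from the protocol for either figure.

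The cost is one or two corrected lines, a pharmacy confirmation and a check of derived documents. No design or analysis element changes.
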